9.2 Analysis of the Key Secondary Efficacy Endpoints

An overview of the analyses for key secondary efficacy is given in Appendix B.

9.2.1 Main Analysis of Key Secondary Efficacy Endpoints CCI

A summary will be provided for the key secondary efficacy endpoints without any imputation of missing data.

Analysis will be as for the main estimation of Estimand 1 with missing values imputed using MI under MAR assumption. Worst values are assumed after use of rescue therapy or treatment discontinuation due to lack of efficacy or AE/death related to study drug prior to imputation. Dichotomous endpoints will be calculated from the underlying imputed variable. The strata-adjusted difference in proportions of responders with 97.5% CI, pooled CMH test p-value will be derived as described in section 9.1.1.

The same MI output dataset as used for the primary endpoint will be used to derive the other dichotomous endpoints from WI NRS (Estimand 2, 3, and 5). CCI

9.2.2 Sensitivity Analysis of Key Secondary Efficacy Endpoints CCI

The following sensitivity analyses will be conducted for the robustness of the main analysis of the key secondary efficacy endpoints:

- Sensitivity Analysis 1: MI using a copy reference (CR) approach under MNAR assumption (dichotomous endpoints will be calculated from the underlying imputed variable); the same MI output dataset for WI NRS using a copy reference (CR) approach under MNAR assumption will be used to derive the other dichotomous

endpoints CCI [REDACTED]. Similarly, the same CR output dataset for SD NRS will feed into all dichotomous endpoints derived from that CCI [REDACTED]

- Sensitivity Analysis 2: “Non-responder” analysis.

See [Appendix C](#) for details about Multiple Imputation.

9.2.3 Impact of COVID-19 on the Key Secondary Efficacy Endpoints CCI [REDACTED]

To assess the impact of COVID-19 related study disruptions (e.g. treatment discontinuation, missing assessments, etc.), the key secondary efficacy endpoints will also be analyzed on the ITT Set excluding subjects affected by COVID-19 related study disruptions. Missing values will be imputed using MI under MAR assumption (dichotomous endpoints will be calculated from the underlying imputed variable). Subjects affected by COVID-19 related study disruptions will not be included in the MI.

9.2.4 Subgroup Analysis of the Key Secondary Efficacy Endpoints CCI [REDACTED]

Summaries for the key secondary endpoints (without imputation of missing data) will be repeated in the subgroups defined in section [4.9](#).

The main analysis for the key secondary efficacy endpoint will be repeated in the subgroups defined in section [4.9](#). The strata-adjusted difference in proportions of responders with 97.5% CI, pooled CMH test p-value will be derived as described in section [9.1.1](#).

MI will not be repeated on each subgroup and missing values will be imputed using the values of MI under MAR assumption on the ITT Set (dichotomous endpoints will be calculated from the underlying imputed variable).

Forest plots with the result of primary analysis and all subgroup analysis of the key secondary efficacy endpoints will be presented.

CCI [REDACTED]
CI [REDACTED]

[REDACTED]

[figure not shown]
[REDACTED]

[REDACTED]

[REDACTED]

[REDACTED]

CCI

Subjects who took rescue therapies or discontinued treatment due to lack of efficacy or AE/death related to study drug will be considered as treatment failures, and all scores after the intake of rescue therapies or treatment discontinuation due to lack of efficacy or AE/death related to study drug will be assigned the worst possible value. In the case of treatment discontinuation for any other reason, a treatment policy strategy will be used and observed after discontinuation data (if available) will be used.

These continuous endpoints will be analyzed using an ANCOVA with treatment group and analysis center as factors and baseline score as covariate. Missing data will be imputed using MI under MAR assumption (see [Appendix C](#) for details about Multiple Imputation).

CCI

Time to onset of effect on pruritus from baseline (defined as the day when the weekly average of WI NRS shows a change from baseline ≥ 4) will be analyzed using Kaplan-Meier survival functions that will be compared between treatment groups by using the log-rank test. The number and proportion of events and censoring, point estimates of the median, Q1 and Q3 with the corresponding 97.5% CI will be presented and Kaplan-Meier curves will also be provided.

The following censoring rules will be applied:

- Subjects who took rescue therapy before achieving onset of effect on pruritus from baseline will be censored and the date of decision to put subject under rescue therapies will be used as censoring date.
- Subjects who discontinued treatment due to lack of efficacy or AE/death related to study drug before achieving onset of effect on pruritus from baseline will be censored and the date of treatment discontinuation will be used as censoring date.
- Subjects who discontinued treatment for any other reason, did not take rescue therapies and did not achieve onset of effect on pruritus from baseline during the study will be censored and date of end of participation will be used as censoring date.
- Subjects who did not take rescue therapies, did not discontinue treatment and did not achieve onset of effect on pruritus from baseline during the study will be censored and date of end of participation will be used as censoring date.

In case of occurrence of both intake of rescue therapy and treatment discontinuation due to lack of efficacy or AE/death related to study drug, the earlier date will be used for censoring purposes.

[figure not shown]
The following rules will be applied:

1 st Intercurrent Event	2 nd Intercurrent Event	Censoring Rule
Intake of rescue therapies	Treatment discontinuation due to lack of efficacy or AE/death related to study drug	Subjects will be censored and the date of decision to put subject under rescue therapies will be used as censoring date
Intake of rescue therapies	Treatment discontinuation for any other reason	Subjects will be censored and the date of decision to put subject under rescue therapies will be used as censoring date
Treatment discontinuation due to lack of efficacy or AE/death related to study drug	Intake of rescue therapies	Subjects will be censored and the date of treatment discontinuation will be used as censoring date
Treatment discontinuation for any other reason	Intake of rescue therapies	Subjects will be censored and the date of decision to put subject under rescue therapies will be used as censoring date

In order to investigate the impact of rescue medication intake and treatment discontinuation, cumulative incidence functions for competing-risks data will be presented and compared between treatment groups by using Gray's test.

Proportion of subjects with an improvement WI NRS ≥ 4 from baseline at Week 1 will be analyzed in the ITT Set, using the Cochran-Mantel-Haenszel (CMH) test stratified by analysis center. The strata-adjusted difference in proportions of responders with 97.5% CI, pooled CMH test p-value will be derived as described in section [9.1.1](#). Subjects who took rescue therapies will be considered as treatment failures, efficacy data collected after the use of rescue therapies will be set to the worst possible value and subject's binary response will be imputed as "Non-responder". Treatment discontinuation due to lack of efficacy, AE/death related to study drug or any other reason is not a factor at this early timepoint since the second administration is not due until Week 4. Missing subject's binary response will be imputed using MI under MAR assumption (dichotomous endpoints will be calculated from the underlying imputed variable). See [Appendix C](#) for details about Multiple Imputation.

[figure not shown]
CCI

CCI

CCI

11 Immunogenicity Analyses

The immunogenicity endpoint is nemolizumab immunogenicity in adult hemodialysis subjects with moderate to severe pruritus.

Anti-drug antibodies assessments using a validated electro-chemiluminescence immunoassay (ECLIA) (screening, confirmatory, titer, Nab) and incidence of positive ADA results (absolute occurrence, percent of subject, and treatment-related ADA) will be summarized by visit and by treatment group. A treatment-related ADA is defined when at baseline, the screening or confirmatory ADA result is negative, and the post-baseline confirmatory ADA result is positive. A corresponding listing will be provided.

Summaries will be based on the Safety Set. Subjects will be summarized according to their actual treatment group.

12 Safety Analysis

Safety assessments/measurements will be conducted for all subjects at the screening visit (upon signing of the ICF) and at every subsequent visit as described in schedule of assessments in [Appendix A](#). All safety assessments/measurements will be listed in by-subject listing.

Subjects will be summarized according to their actual treatment group.

TEAEs will be summarized descriptively overall and by treatment and other safety information will be summarized descriptively by treatment.

All safety analyses will be based on the Safety Set.

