An independent data monitoring committee (IDMC) will review and monitor subject safety throughout the study. The study team will remain blinded until the end of the study.

An independent adjudication committee (IAC) will review and adjudicate all asthma-related AEs.

Selection of Subjects:	
Main Inclusion Criteria:
 
 1. Subjects aged ≥ 18 years at the screening visit. 2. Has end-stage kidney disease (ESKD) and have been on hemodialysis three times per week for at least three months prior to the start of screening. 
Note 1: Subjects who require an occasional additional hemodialysis treatment to manage fluid overload may be enrolled as long as it is anticipated that no more than one such treatment will be required in any given week.
 
Note 2: Subjects having received in-home hemodialysis may participate as long as they have switched to in-center hemodialysis at least two weeks prior to screening and plan to remain on in-center hemodialysis for the duration of the study.
 
 3. Hemodialysis subjects meeting the Kidney Outcome Quality Initiative Guidelines of hemodialysis adequacy within 60 days of screening, two: 
 • Single-pool Kt/V measurements of at least 1.2. 4. Pruritus for \geq three months (documented pruritus with no etiology identified other than CKD by medical record, previous physician's letter/statement, or written documentation by site investigators based on the medical history obtained from the subject). 5. WI NRS score ≥ 5.0 at the screening and baseline visit. Screening WI NRS score will be determined by a single WI NRS assessment (score ranging from 0 to 10) for the 24-hour period immediately preceding the screening visit. Baseline WI NRS score will be determined based on the weekly average of daily WI NRS scores (score ranging from 0 to 10) during the seven days immediately preceding
-------------------------------	---

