15.1 Worst Itch Numeric Rating Scale

The WI NRS is a scale to be used by the subjects to report the intensity of their worst pruritus (itch) during the last 24 hours (see [Appendix 3](#)). The WI NRS is a validated measurement tool and has been used to assess subject-reported severity of itch in CKD-aP clinical trials ([Fishbane 2020](#)).

Subjects will be asked the following question:

- For worst itch intensity: “On a scale of 0 to 10, with 0 being ‘no itch’ and 10 being the ‘worst itch imaginable’, how would you rate your itch at the worst moment during the previous 24 hours?”

The screening WI NRS score will be determined by a single WI NRS assessment (score ranging from 0 to 10) for the 24-hour period immediately preceding the screening visit. The baseline WI NRS score will be determined based on the weekly average of daily WI NRS scores (score ranging from 0 to 10) during the seven days immediately preceding baseline (rounding is not permitted). A minimum of four daily scores out of the seven days immediately preceding baseline is required for this calculation.

Subjects will record their 24-hour worst itching assessment scores on all days. Subjects will receive instructions on how to record their WI NRS scores and will complete the assessment once daily in the evening throughout the clinical study (including the screening and the follow-up period) in an eDiary. If they cannot record it in the evening, then record it in the following morning is acceptable.

If a subject does not complete the WI NRS assessments in the evening, the subject will be allowed to complete the assessments the following morning.

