Baseline is defined as the last non-missing measurement prior to the first treatment injection at Day 1/Baseline for subjects randomized and treated or prior to the randomization for subjects randomized but not treated (if any). Change from baseline and percent change from baseline are defined as follows:

$$\text{Change from Baseline} = \text{PostBaseline} - \text{Baseline}$$

$$\text{Percent Change from Baseline} = \begin{cases} \text{Baseline} \neq 0 \Rightarrow 100 \cdot \frac{\text{PostBaseline} - \text{Baseline}}{\text{Baseline}} \\ \text{Baseline} = 0 \Rightarrow \text{Missing} \end{cases}$$

All by-visit summaries and analyses will use the analysis visit (see section 4.10).

Continuous data will be summarized using the following descriptive statistics: number of subjects (n), mean, standard deviation (SD), median, first and third quartiles (Q1 and Q3), minimum and maximum. Categorical data will be summarized using the frequency count (n) and percentage (%) of subjects for each category. For the summary statistics of all numerical variables unless otherwise specified, minimum and maximum will be displayed to the same level of precision as reported. Mean, median, Q1 and Q3 will be displayed to one level of precision greater than the data collected. Standard deviation will be displayed to two levels of precision greater than the data collected.

P-values will be displayed in the following format, 0.9999. Any p-value less than 0.0001 will be displayed as <0.0001. Any p-value greater than 0.9999 will be displayed as >0.9999.

The following flagging conventions will be applied for the p-values of all statistical testing:

- $0.01 \leq p\text{-values} < 0.025$ will be flagged with one asterisk (e.g. “0.0249 *”).
- $0.001 \leq p\text{-value} < 0.01$ will be flagged with two asterisks (e.g. “0.0099 **”).
- $0.0001 \leq p\text{-value} < 0.001$ will be flagged with three asterisks (e.g. “0.0009 ***”).
- $p\text{-value} < 0.0001$ will be flagged with four asterisks (e.g. “<0.0001 ****”).

When count data are presented, the percentage will be suppressed when the count is zero in order to draw attention to the non-zero counts. The denominator for all percentages will be the number of subjects in that treatment within the analysis set of interest, unless otherwise specified. Percentages will be presented to one decimal place.

All proportions will be presented as percentages (not as fraction of unit).

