Estimand 1: In adult hemodialysis patients with chronic kidney disease and associated moderate to severe pruritus, 2 nemolizumab dosing schedules ^[1] compared to placebo by the difference in proportions of responders where response is defined as an improvement from baseline of WI NRS ≥ 4 at Week 12 without use of rescue therapies and without treatment discontinuation due to lack of efficacy or AE/death related to study drug	
Treatment Conditions: initial dose of nemolizumab (60 mg) or placebo at baseline, then nemolizumab (30 mg or 60 mg) or placebo Q4W at Weeks 4 and 8 via subcutaneous injection.
 
Population: adult hemodialysis patients with chronic kidney disease and associated moderate to severe pruritus (will be estimated in the Intent-to-Treat analysis set).
 
Variable: a binary composite response where: Responder is defined as an improvement ≥ 4 in WI NRS from baseline at Week 12 without use of rescue therapies and without treatment discontinuation due to lack of efficacy or AE/death related to study drug. Non-responder is defined as an improvement < 4 in WI NRS from baseline at Week 12 or use of rescue therapies or treatment discontinuation due to lack of efficacy or AE/death related to study drug.
 
Strategies for Intercurrent Events: A composite strategy was chosen for the use of rescue therapies and treatment discontinuation due to lack of efficacy or AE/death related to study drug; in case of use of rescue therapies or treatment discontinuation due to lack of efficacy or AE/death related to study drug, subjects will be considered as treatment failures in the binary composite response. In the case of treatment discontinuation for any other reason, a treatment policy strategy will be used and observed after discontinuation data (if available) will be used.
 
Summary measure: treatment difference of nemolizumab versus placebo in proportions of responders

[1] Dosing schedules compared to placebo Q4W are an initial SC dose of nemolizumab (60 mg) at baseline then either 30 mg or 60 mg Q4W at Week 4 and Week 8.

Summary of estimation is provided in section [Appendix B](#).

Composite binary response variables are defined in a similar manner as in the primary efficacy estimand for the following key secondary estimands where all estimands attributes are as per Estimand 1 except for the variable definition as reported below.

Table 7 Estimands for Key Secondary Efficacy Endpoints

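### The SAP's time-to-onset event is written as a rise of at least 4 points in WI NRS, so under the SAP's own sign convention it counts worsening and not improvement

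*SAP*

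**What the plan says.** Three statements have to be read together.

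- **The event.** The time-to-onset paragraph stands in SAP section 9, after section 9.2.4, under a heading that is redacted. The endpoint is "defined as the day when the weekly average of WI NRS shows a change from baseline" of ≥ 4. It is analysed with Kaplan-Meier curves and a log-rank test, and then with cumulative incidence functions and Gray's test.
- **The sign of change.** SAP section 4 (General Statistical Considerations) states, for the whole plan, "Change from baseline and percent change from baseline are defined as follows". The formula that follows subtracts the baseline value from the post-baseline value.
- **The scale.** Protocol section 15.1 gives the WI NRS question as "On a scale of 0 to 10, with 0 being ‘no itch’ and 10 being the ‘worst itch imaginable". A higher score is worse, so benefit is a negative change.

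For comparison, the primary estimand (SAP section 5, Table 6) states the direction: "Responder is defined as an improvement ≥ 4 in WI NRS from baseline at Week 12". So does the Week 1 analysis a little further on in section 9: "Proportion of subjects with an improvement WI NRS ≥ 4 from baseline at Week 1".

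**The concern.** The sentence is the operative definition of the event for four planned outputs, not background text. A programmer who takes the derived change variable and applies the printed threshold would flag deterioration as onset of effect and would leave every 4-point responder without an event. If the programmer instead assumes the intended direction, the analysis departs from its written specification and nothing on file explains why. Protocol section 19 says that the SAP prevails where the two documents differ, so wording elsewhere would not correct it automatically.

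**Working it through.** No sample size, power or alpha figure in the plan depends on this definition, so there is no stated number to reproduce. The check is sign arithmetic.

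**Inputs**
- Change = post − baseline (SAP section 4).
- Scale limits 0 and 10, with 10 the worst (Protocol section 15.1).
- Entry rule: "WI NRS score ≥ 5.0 at the screening and baseline visit" (Protocol synopsis and section 11.2, criterion 5).
- Event as written: change ≥ 4 (SAP section 9).

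**Step 1: single subjects**

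| Baseline → post | Change | Event as written (≥ 4) | Improvement event (≤ −4) |
|---|---|---|---|
| 8 → 3 | 3 − 8 = −5 | no | yes |
| 8 → 4 | 4 − 8 = −4 | no | yes |
| 6 → 2 | 2 − 6 = −4 | no | yes |
| 6 → 10 | 10 − 6 = +4 | yes | no |
| 5 → 9 | 9 − 5 = +4 | yes | no |

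**Step 2: who can have the event**

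For baseline B the largest possible change is 10 − B. The written event needs 10 − B ≥ 4, so B ≤ 6. The improvement event needs a post-baseline score of at most B − 4, which is possible whenever B ≥ 4.

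| Baseline | Largest change (10 − B) | Post score needed as written (B + 4) | Reachable | Post score needed for improvement (at most B − 4) |
|---|---|---|---|---|
| 5.0 | +5.0 | 9.0 | yes | 1.0 |
| 5.5 | +4.5 | 9.5 | yes | 1.5 |
| 6.0 | +4.0 | 10.0 | yes | 2.0 |
| 6.01 | +3.99 | 10.01 | no | 2.01 |
| 7.0 | +3.0 | 11.0 | no | 3.0 |
| 8.0 | +2.0 | 12.0 | no | 4.0 |
| 10.0 | 0.0 | 14.0 | no | 6.0 |

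Among subjects who meet the entry rule, only baselines from 5.0 to 6.0 can have the event as written, and they need a weekly average between 9 and 10. Nobody in the more severe baseline subgroup of SAP section 4.9 (above 7) could ever have it. With the sign corrected, the event is reachable from every eligible baseline, 5 to 10.

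**Step 3: can the word change be read without a sign?**

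The SAP uses signed change elsewhere. Section 12.9 sorts percent change in peak expiratory flow into bands running from −20% or lower to +20% or higher. An absolute value would not help either, because it would count worsening and improvement alike.

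**The case against.** The strongest reply is that nobody would misread the sentence. The endpoint is called an onset of effect, subjects are described as *achieving* it, and rescue or discontinuation for lack of efficacy beforehand leads to censoring. None of that fits a deterioration endpoint. This stands: the intent is clear, and the defect is one of wording rather than of analysis concept. It does not make the printed rule correct.

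Three further points also stand.

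- The documents use an unsigned threshold as shorthand elsewhere. The general paragraph in SAP section 9 on weekly averages (and Protocol section 19.3) refers to proportions with WI NRS ≥ 4 without mentioning improvement. The time-to-onset sentence is therefore not the only place where the direction is left out. The difference is that the shorthand refers to endpoints defined as improvement elsewhere, whereas here the sentence is the only visible definition.
- Text just before the paragraph, and the lists of further efficacy endpoints, are redacted. SAP section 17 leaves detailed specifications, including code, to table shells that are not part of these documents. A direction may be stated in either place. The visible sentence is complete, though, and it conflicts with an unredacted general rule.
- The endpoint is outside the testing hierarchy of SAP section 4.4.

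A reader might infer that literal programming would give reversed curves, with the poorer arm appearing to respond sooner. The documents do not support that. Only baselines of 5.0 to 6.0 could contribute events, and the worst-possible scores assigned after rescue or after discontinuation for lack of efficacy or a related adverse event would add none to the Kaplan-Meier analysis, because those subjects are censored at that point. The more likely product is an analysis with almost no events, which programming checks would probably catch.

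**Conclusion.** Wrong as written. Under the SAP's own definition of change, the time-to-onset event is a worsening of at least 4 points, open only to eligible subjects with baselines from 5.0 to 6.0, and improvement of any size never triggers it.

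The reach is limited to Tables 14.2.14.1 and 14.2.14.3 and Figures 14.2.14.2 and 14.2.14.4, with their log-rank and Gray's tests. A reader might infer a threat to the main efficacy conclusions. There is none: the primary and key secondary endpoints are defined as improvement, and neither the alpha allocation nor the sample size uses this definition.

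The conclusion rests on two assumptions: that the section 4 formula applies here, since no other sign rule is visible, and that subjects meet the entry threshold of 5.0. A subject randomized in breach of that threshold could also reach the written event. The remark that a literal analysis would be nearly free of events is a judgement, because the documents give no distribution of baseline scores or of worsening.

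**What to change.** In the time-to-onset definition in SAP section 9, replace *a change from baseline ≥ 4* with *an improvement (decrease) from baseline ≥ 4, i.e. change from baseline ≤ −4*. Check that the shells and code for the four outputs use the same direction.

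The cost is one phrase in the SAP, best changed before unblinding. No data collection, sample size or testing order changes. The sign error does not by itself call for a new rule on how the onset day is dated, and none is proposed here.

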13.2.1 Early Termination Visit

Subjects who prematurely discontinue from the study should complete an early termination (ET) visit at the time of discontinuation. A follow-up/final visit is required 12 weeks after the last study drug administration.

Subjects who prematurely discontinue the study treatment will be asked to continue participation in the study and return for all remaining visits and assessments.

Participation will continue until the subject completes the final study visit or otherwise discontinues study participation.

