All efficacy analyses will be performed in the ITT Set. The primary efficacy analysis will be repeated in the mITT Set and PP Set as supportive evidence and to assess robustness of efficacy findings.

Subjects will be summarized and analyzed according to their randomized treatment group.

Summaries based on observed case (OC) will be provided for all primary, secondary, and exploratory efficacy endpoints without imputation of any missing data. For the OC summaries, if any rescue therapy is received or treatment is discontinued, and data are collected post-rescue receipt or treatment discontinuation, then the data post-rescue or post-discontinuation will be summarized as observed.

Proportion of subjects with WI NRS/SD NRS ≥ 4 and WI NRS ≥ 3 , changes and percent changes from baseline of WI NRS/SD NRS at each week (from week 1 through week 20) will be calculated on the basis of the weekly average, obtained by averaging at least 4 daily WI NRS/SD NRS scores over 7-day periods.

For baseline weekly average, if fewer than 4 daily WI NRS/SD NRS scores for the 7-day period are available, the interval lower bound will be extended up to 7 additional days, one day at a time, until 4 daily WI NRS/SD NRS scores are available. If after the interval extension fewer than 4 daily WI NRS/SD NRS scores are available, the baseline weekly average WI NRS/SD NRS will be considered missing.

For week 12 weekly average, if fewer than 4 daily WI NRS/SD NRS scores for the 7-day period are available, the interval upper bound will be extended for 5 additional days, one day at a time, until 4 daily WI NRS/SD NRS scores are available. If after extending the upper bound fewer than 4 daily WI NRS/SD NRS scores available, the interval lower bound will be extended for 5 additional days, one day at a time, until 4 daily scores are available. If after the interval extension fewer than 4 daily WI NRS/SD NRS scores are available, the week 12 weekly average WI NRS/SD NRS will be considered missing.

For all the other weekly averages, if fewer than 4 daily WI NRS/SD NRS scores for the 7-day period are available, the weekly average WI NRS/SD NRS will be considered missing for that period.

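### Time to onset of itch effect: event-free subjects are censored at the end of participation rather than at their last evaluable weekly average, so time after a diary stops counts as time without onset.

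*SAP*

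**What the plan says.** The time-to-onset text is in SAP Section 9, after 9.2.4. The event is "defined as the day when the weekly average of WI NRS shows a change from baseline" of at least 4 points. The analysis uses Kaplan-Meier curves, a log-rank test, and the median and quartiles with 97.5% intervals. Cumulative incidence functions with Gray's test are added to look at rescue and treatment discontinuation.

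There are four censoring rules for subjects without onset:

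- After rescue, "the date of decision to put subject under rescue therapies will be used as censoring date".
- After discontinuation for lack of efficacy or a related AE/death, "the date of treatment discontinuation will be used as censoring date".
- The other two rules cover subjects without rescue who stopped treatment for another reason or did not stop. Those who "did not achieve onset of effect on pruritus from baseline during the study will be censored and date of end of participation will be used" for the censoring date.

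The opening text of SAP Section 9 sets the data requirement. Outside baseline and Week 12, where the window may be extended, a week with fewer than 4 daily scores means that "the weekly average WI NRS/SD NRS will be considered missing for that period".

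The diary is planned "once daily in the evening throughout the clinical study (including the screening and the follow-up period) in an eDiary" (Protocol 15.1). On treatment discontinuation, Protocol 13.2.1 states: "Subjects who prematurely discontinue the study treatment will be asked to continue participation in the study and return for all remaining visits and assessments".

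**The concern.** The event is read from the diary, but the censoring date is read from study participation, and the two can end at different times. A subject who stops the diary at Week 5 and attends the Week 20 visit stays in the risk set as known event-free for 15 weeks in which onset could not have been recorded. A subject with no post-baseline weekly average, or no baseline average, counts as event-free throughout.

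The plan itself expects diary gaps. It has a 4-of-7 rule, window extensions, and three sensitivity analyses of the primary endpoint using at least 3, 2 or 1 scores.

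No visible text fills the gap by imputation. The neighbouring ANCOVA and Week 1 responder paragraphs both state multiple imputation, and the time-to-onset text does not. In SAP Appendix F, outputs 14.2.14.1 to 14.2.14.4 lack the imputation label that 14.2.12.2 and 14.2.15.1 carry. SAP 4.7 also limits the main imputation to data up to Week 12, while this analysis runs to the end of participation.

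At stake are the onset curves, their quartiles and the log-rank p-value. That p-value would carry an asterisk below 0.025 under the flagging rule in SAP Section 4.

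**Working it through.** **The plan's own figure.** The documents give no figure for time to onset. The nearest is the primary endpoint (SAP 4.2): 84 per group, 20% v 50%, two-sided alpha 0.025, power at least 90%. Using z = (0.30·√84 − 2.241·√(2·0.35·0.65)) / √(0.2·0.8 + 0.5·0.5) = (2.750 − 1.512)/0.640 = 1.93, power is 97.3%, so the statement holds. I borrow 50% and 20% below as illustrative onset by Week 12.

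**Assumptions not in the documents.** Weekly onset chance h is constant. A share f of diaries stops early, independently of onset, while participation runs to Week 20. There is no rescue or failure-type censoring.

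**Formula.** Nobody is then censored before Week 20, so Kaplan-Meier onset at Week 12 is simply the share of subjects with a seen onset:

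read onset = (1 − f)·p + f·g

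Here p is true Week 12 onset, and g is the mean of min(1 − (1 − h)^D, p) over the last evaluable week D.

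For p = 50%, h = 1 − 0.5^(1/12) = 0.0561. If D is uniform over Weeks 0-11, g = 0.258. Over Weeks 0-19, g = (12/20)·0.258 + (8/20)·0.5 = 0.355. Over Weeks 0-7, g = 0.176. Example at f = 30% and Weeks 0-11: 0.7·0.5 + 0.3·0.258 = 42.7%.

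| Last evaluable week | f = 5% | 10% | 20% | 30% |
|---|---|---|---|---|
| True 50%, Weeks 0-19 | 49.3% | 48.5% | 47.1% | 45.6% |
| True 50%, Weeks 0-11 | 48.8% | 47.6% | 45.2% | 42.7% |
| True 50%, Weeks 0-7 | 48.4% | 46.8% | 43.5% | 40.3% |
| True 20%, Weeks 0-19 | 19.7% | 19.4% | 18.7% | 18.1% |
| True 20%, Weeks 0-7 | 19.3% | 18.6% | 17.2% | 15.9% |

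Simulation with 400,000 subjects per scenario agreed within about 0.1 point for the Weeks 0-19 and 0-7 rows. Censoring at the last evaluable week returned 50% and 20% to within 0.1 point. At f = 0 the two rules coincide.

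**Log-rank test.** Simulated with 84 per arm, alpha 0.025 and stops over Weeks 0-19. The first three rows use 50% v 20% onset (2,000 runs); the last uses 50% in both arms (3,000 runs).

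| Diary stop, active / placebo | End of participation | Last evaluable week |
|---|---|---|
| 30% / 30% | power 98.7%, log-HR 1.08 | power 99.2%, log-HR 1.13 |
| 30% / 10% | log-HR 0.98 | log-HR 1.17 |
| 10% / 30% | log-HR 1.22 | log-HR 1.11 |
| no true effect, 10% v 30% | error 6.1% | error 2.4% |

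Equal loss barely affects the test. Unequal loss shrinks or inflates the contrast, depending on which arm loses more, and can raise the error rate above the nominal 2.5%.

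**The case against.** The strongest reply is that early censoring recovers the truth here because diary stop was assumed independent of onset, which is the condition under which it is unbiased. Suppose instead that nobody whose diary stops would have had a later onset. The SAP rule is then correct: with stops over Weeks 0-11, true onset is 47.6% at f = 10% and 42.7% at f = 30%, and the alternative overstates it at 50%. Counting unseen time as no onset also resembles the non-responder analyses elsewhere in the SAP. This stands as a reason to keep the present rule as a sensitivity analysis. As the main rule, it asserts that every unobserved week was free of onset.

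The size is also open to challenge, and fairly. All stop rates are assumed. The 50% and 20% are Week 12 responder rates, not first-onset rates. The protocol (8.3.1) reports marked improvement in all groups by Week 4 of the phase 2a study, and front-loaded onset reduces the loss. With about 76% of Week 12 onset reached by Week 4 and stops within the first 12 weeks, a true 50% reads as 48.7%, 47.3% and 46.0% at f = 10%, 20% and 30%.

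A reader might infer that the published onset curve will necessarily be too low. The documents do not support that. Diaries are planned through follow-up, and with complete diaries the bias is zero. Censoring at rescue or failure tends to raise Kaplan-Meier onset, so the net direction for the whole curve is not fixed.

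Appendix C and parts of Section 9 are blacked out, so a missing-week rule there cannot be excluded. The visible rules nevertheless name an explicit date.

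**Conclusion.** The point holds as a fault in one stated rule. If diaries stop before participation ends, the end-of-participation date turns unobserved time into event-free time. That component lowers Kaplan-Meier onset, and it biases the log-rank comparison in either direction if diary loss differs by arm. For 5-30% stops independent of onset and a constant weekly onset chance, a true 50% at Week 12 reads as about 49% down to 43-46%, or about 40% with early stops. None of these stop rates comes from the documents.

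Severity is low. A reader might infer a threat to the trial's main conclusions, but time to onset is not in the testing sequence of SAP 4.4, so the primary and key secondary results are untouched.

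**What to change.** In the last two censoring rules, replace the end-of-participation date with the target study day (SAP Table 4) of the last non-missing weekly average WI NRS. Use Day 1 if there is no post-baseline average or the baseline average is missing. Apply the same date in the cumulative incidence analysis to subjects with neither an event nor a competing event.

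Keep the end-of-participation rule as a sensitivity analysis. A last-average date still carries a subject through a long gap between evaluable weeks, for example averages at Weeks 5 and 20 only. Add a sensitivity analysis that censors at the last average before such a gap, with the gap length fixed in advance.

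The cost is a few lines of SAP text and one derived date, with no new data. The downside is slightly shorter follow-up for some censored subjects and reliance on diary stop being non-informative, which the retained sensitivity analysis helps to examine.
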